7.8.1 Adverse Event occurrence rate

The occurrence rate of a given AE (i.e. proportion of subjects who experienced an AE) will be calculated by dividing the number of subjects who experienced this AE by the total number of subjects in the Safety set.

When calculating occurrence rates, if a subject has the same AE preferred term reported more than once, then the subject will be reported only once using the worst AE attribute.

Occurrence rate will be presented overall and by worst severity level (i.e. in case a patient experienced several times the same AE, only the worst severity level will be presented in the summary table by severity category).

7.8.2 Adverse Events Tabulation

Calculated AE duration will be indicated in the listing.

Onset day of an AE will be calculated if both the AE start date and date of dosing are complete and is calculated as:

- Onset day for AE = (AE start date – Date of first dose) + 1 (only if AE start date \geq First dose date)

Duration of an AE will be calculated if both the AE stop and start dates are complete and is calculated as:

- Duration of an AE = (AE stop date – AE start date) + 1

In cases where the start date of an AE is completely known but the AE has not yet resolved at the end of the study, duration of an AE will be calculated as:

- Duration of an unresolved AE = (Study termination date – AE start date) + 1

These observations will be flagged in listings with a greater than sign (i.e. $>$) prior to presentation of the duration.

In case of AE partial dates: if only the day is missing then the first day of the month will be used for start dates and the last day of the month will be used for end dates. In case the AE started on the same month than the first dose and the AE start day is missing, the partial date will be replaced by the first dose date.

If the month is missing no imputation will be done.

If duration of an AE cannot be calculated, the information will be missing from the listing.

Incidence rates, frequencies and summary tabulations will be provided for:

- All TEAEs
- All Treatment Emergent Serious AEs (TESAEs)
- All Treatment Emergent Serious AEs (TESAEs) by severity
- All TEAEs leading to permanent treatment discontinuation
- All TEAEs by severity
- All TESAEs by drug-event relationship
- All TEAEs by drug-event relationship
- All TEAEs leading to death

7.9 Safety Laboratory Evaluation

Summary statistics (n, mean, SD, median, quartiles, minimum, maximum) will be presented at each assessment time point for each continuous laboratory assessment, including routine haematology, chemistry and urinary panels. Summary statistics changes from baseline will also be presented. For categorical variables the outputs will be generated according to the section 7.1.1.

For the classification of abnormal laboratory values, the individual normal range of the laboratory will be used.

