## **Laboratory Tests**

Laboratory tests (haematology, coagulation, blood chemistry and urinalysis) will be monitored before and during the study days mentioned in the study chart. A total volume of 100ml will be collected during the study. For each patient participating to the dosimetric and PK sub-study a total of 205 ml will be drawn throughout the study.

Descriptive statistics including shift tables will be generated for all laboratory tests performed i.e. the actual values and the changes from pre-injection by cross-tabulations (with classes for below, within, and above normal range).

Laboratory data will be analysed with respect to the normal ranges of values provided by the local laboratory and with respect to pre-defined levels of change in these values.

Abnormal laboratory test results will be tabulated.

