6.1 Safety endpoints (Primary)

Safety endpoints will be evaluated by:

1. Serious and non-serious adverse event assessments
2. Abnormal haematology, coagulation, blood chemistry, urinalysis laboratory tests
3. Change from baseline of ECG parameters (including HR heart rate, RR interval, PR interval, QRS width and QT interval)
4. Change from baseline of vital signs

6.2 Pharmacokinetics and Dosimetry (Secondary - only for patients participating to the dosimetry and pk substudy)

Pharmacokinetics and dosimetry will be assessed by:

1. Serial measurements of rhAnnexin V-128 concentrations (by ELISA) from serum samples
 - a. Annexin concentrations in serum
 - b. Annexin PK parameters: AUC, Vz, Cl and elimination t_{1/2}
2. Serial measurements of radioactivity in whole blood and serum samples
 - a. Whole blood and serum concentrations of total radioactivity
 - b. Whole blood and serum PK parameters for total radioactivity: AUC, t_{1/2}
3. Serial measurements of radioactivity in urine samples
 - a. % excretion of total radioactivity in urine
 - b. SEC-HPLC analysis – as a function of time to assess chemical status and presence of Annexin related species
4. Radiation dose to the organ of interests (particularly the kidneys), effective dose equivalent and effective dose

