10 APPENDICES

10.1 List of tables

Number	Table Title	Analysis set
14.1.1	Subject Disposition	Screened
14.1.2	Summary of Protocol Deviations	Safety
14.1.3	Demographics and Baseline Characteristics	Safety
14.1.4	Medical History	Safety
14.1.5	Prior Medications	Safety
14.1.6	Concomitant Medications	Safety
14.1.7	Extent of Exposure: Summary of injected Dose of the investigated imaging product.	Safety
14.2.1	Blood and serum concentrations of total radioactivity	PK
14.2.2	Blood and serum area under the concentration-time curve (AUC) and terminal half-life (t _{1/2}) of total radioactivity after intravenous 99mTc-rhAnnexin V-128	PK
14.2.3	Summary of Percent excretion of total radioactivity in urine	PK
14.2.4	Summary of Serum concentrations of rhAnnexin V-128 based on ELISA analysis	PK
14.2.5	Summary of Volume of distribution (V _z) and systemic clearance (Cl) of rhAnnexin V-128 based on ELISA analysis	PK
14.2.6	Summary of SEC-HPLC analysis results	PK
14.3.1.1	Overall Summary of TEAEs	Safety
14.3.1.2	Occurrence of TEAEs – Number and percentage of subjects by System Organ Class and Preferred Term	Safety
14.3.1.3	Occurrence of Serious TEAEs – Number and percentage of subject by System Organ Class and Preferred Term	Safety
14.3.1.4	Occurrence of TEAEs Leading to permanent treatment discontinuation – Number and percentage of subject by System Organ Class and Preferred Term	Safety
14.3.1.5	Occurrence of Serious TEAEs Severity – Number and percentage of subject by System Organ Class and Preferred Term	Safety
14.3.1.6	Occurrence of Serious TEAEs Relationship to study drugs – Number and Percentage of Subjects by System Organ Class, and Preferred Term	Safety

Number	Table Title	Analysis set
14.3.1.7	Occurrence of TEAEs Relationship to study drugs – Number and Percentage of Subjects by System Organ Class, and Preferred Term	Safety
14.3.1.8	Occurrence of TEAEs Severity – Number and Percentage of Subject by System Organ Class and Preferred Term	Safety
14.3.2	Listing of Deaths and Other Serious Adverse Events	Safety
14.3.4.1	Listing of Laboratory Safety Values for Subjects with Clinically Significant Abnormal Laboratory Values	Safety
14.3.4.2	Haematology parameters at each visit and change from baseline	Safety
14.3.4.3	Biochemistry parameters at each visit and change from baseline	Safety
14.3.4.4	Urinalysis parameters at each visit and change from baseline	Safety

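### The SAP drops the laboratory shift tables the protocol requires, plans no count of subjects with abnormal blood results although these are a primary safety endpoint, and declares no change

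*SAP*

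**What the plan says.** **Protocol, section 8, Laboratory Tests.** "Descriptive statistics including shift tables will be generated for all laboratory tests performed", as cross-tabulations with classes below, within and above the normal range. In addition, "Abnormal laboratory test results will be tabulated". The assessment is also to be made "with respect to the normal ranges of values provided by the local laboratory and with respect to pre-defined levels of change in these values".

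**SAP 6.1.** Item 2 of the primary safety endpoints is "Abnormal haematology, coagulation, blood chemistry, urinalysis laboratory tests". SAP 7.7 likewise says that safety is judged on abnormal renal, hepatic and coagulation tests.

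**SAP 7.9.** Summary statistics at each time point are planned "for each continuous laboratory assessment, including routine haematology, chemistry and urinary panels", with changes from baseline. Categorical variables are referred to 7.1.1. The section ends: "For the classification of abnormal laboratory values, the individual normal range of the laboratory will be used".

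**SAP 10.1.** There are four laboratory outputs. Table 14.3.4.1 is a "Listing of Laboratory Safety Values for Subjects with Clinically Significant Abnormal Laboratory Values". Tables 14.3.4.2 to 14.3.4.4 give haematology, biochemistry and urinalysis values with change from baseline.

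**SAP 7.19** states that the planned analysis did not change.

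**The concern.** Endpoint 2 is abnormality itself, whereas endpoints 3 and 4 (ECG and vital signs) are changes from baseline. The SAP nevertheless gives vital signs a shift table (14.3.8.2) and ECG a normal/abnormal table with n (%) (14.3.9.1), and gives blood tests neither. It states which range defines an abnormal value, but no summary table for blood tests then uses that definition.

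Two things are at stake. First, the report would have no tabulated answer to how many subjects were abnormal on a given blood test, or how many went from normal before injection to abnormal afterwards. Second, an analysis specified in the protocol for a primary endpoint would disappear while the SAP states that nothing was altered.

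**Working it through.** **1. Protocol requirements against SAP outputs**

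| Protocol section 8 requires | SAP provides |
|---|---|
| Low/normal/high shift tables, all laboratory tests | None in 7.9, the list of tables or the shells. The only shift table is 14.3.8.2, vital signs |
| Tabulation of abnormal results | 14.3.4.1 in part: a listing without n (%), limited to clinically significant values |
| Analysis against pre-defined levels of change | No levels and no output |
| Descriptive statistics and change from pre-injection | 14.3.4.2 to 14.3.4.4 |

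The only laboratory shell that shows n (%) by category is for urine dipstick protein, positive or negative. SAP 7.1.1 places abnormal flags in the individual listings.

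**2. Unscheduled and repeat tests.** SAP 7.1.2 keeps these out of the by-visit statistics and sends them to assessments of maximum and minimum change, shift tables and listings. No laboratory shift table or maximum/minimum-change table is planned, so an abnormal unscheduled blood result reaches no laboratory summary table.

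**3. Can the planned statistics replace the count?** The documents give no laboratory data, so this uses constructed values at the planned n of 20 and an assumed upper limit of normal of 40.

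- Set A: 18, 18, 18, 18, 24, 24, 24, 24, 25, 30, 30, 30, 38, 38, 38, 40, 40, 40, 40, 46
- Set B: 18, 18, 18, 18, 24, 24, 24, 24, 25, 30, 30, 33, 35, 35, 37, 41, 41, 41, 41, 46

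For both sets:

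- Sum 603, so mean = 603/20 = 30.15.
- Sum of squares 19773, so SD = sqrt((19773 − 603²/20)/19) = sqrt(1592.55/19) = 9.16.
- Q1 (ranks 5 and 6) = 24; median (ranks 10 and 11) = 30.
- Q3 (ranks 15 and 16) = (38 + 40)/2 = 39 in A and (37 + 41)/2 = 39 in B.
- Minimum 18, maximum 46.

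Above 40: A has 1 of 20 (5%), B has 5 of 20 (25%).

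Change-from-baseline statistics do not separate the sets either if, say, every subject had a baseline of 25. Each change is then the value minus 25, and the mean change is 30.15 − 25 = 5.15 in both.

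The contrast depends on where the limit falls:

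| Assumed upper limit | Above limit, A | Above limit, B |
|---|---|---|
| 37 | 3 + 4 + 1 = 8 | 4 + 1 = 5 |
| 39 | 4 + 1 = 5 | 4 + 1 = 5 |
| 40 | 1 | 4 + 1 = 5 |
| 41 | 1 | 1 |

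Under linear interpolation Q3 would be 38.5 in A and 38 in B. The haematology shell, which biochemistry shares, prints n, mean, SD, median, minimum and maximum without quartiles. On that shell's raw-value columns the sets are identical.

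**4. Would abnormal counts by visit be enough?** Suppose 3 of 20 subjects are abnormal at baseline and 3 of 20 at Day 30, and k of them are the same people. Newly abnormal = 3 − k with k from 0 to 3, so the number lies between 0 and 3. Only the cross-tabulation settles it.

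**The case against.** The strongest reply is that the SAP can be read more generously. SAP 7.9 sends categorical variables to 7.1.1, which prescribes frequencies and percentages, and then says how abnormal values are classified; that classification could be one of those variables. SAP 7.1.2 also mentions shift tables without limiting them to vital signs. On this reading the list of tables is incomplete and no analysis was dropped. That may explain how the gap arose, but it does not close it: 7.1.1 assigns the abnormal flags to listings, and neither the list of tables nor the shells contain a laboratory shift table or a count of abnormal blood results.

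Several points of the reply do stand:

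- Abnormal results are partly covered. Table 14.3.4.1 shows the clinically significant ones, and those reported as adverse events enter the AE tables with n (%).
- All values are listed with flags and ranges. SAP 4.2 says recruitment stopped with 80% or more of the planned sample evaluable, that is at least 0.80 × 20 = 16 subjects, so hand counting is feasible.
- The protocol says abnormal results will be tabulated; it does not prescribe n (%) of subjects. The margins of a shift table would largely supply that count.
- The numerical example is constructed. It shows that summary statistics need not reveal the count, not that they would hide it in this trial. A maximum of 46 against a limit of 40 already shows at least one abnormal subject.
- The safety analysis is descriptive, with no formal test on laboratory results.

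**Conclusion.** The concern holds. Followed as written, the SAP omits the protocol's shift tables for all laboratory tests and meets its tabulation of abnormal results only in part, for a component of the primary safety endpoint, while 7.19 declares no change. This rests on a direct comparison of the documents and needs no assumption.

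The illustration of size (1 versus 5 abnormal subjects of 20; 0 to 3 newly abnormal) does rest on assumed values and an assumed limit, and should be read only as proof that the planned summaries do not determine the missing results.

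The consequence is moderate. No data are lost and the counts can be rebuilt from the listings, but the report would leave that work to its reader and would not disclose the departure from the protocol.

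**What to change.** 1. Add to SAP 7.9, the list of tables and the shells: low/normal/high shift tables from baseline, and n (%) of subjects with abnormal results by test, for haematology, coagulation, chemistry and urinalysis. Include unscheduled and repeat values in the shift tables, as 7.1.2 already provides. The vital-signs shell 14.3.8.2 can serve as the template.
2. Correct 7.19 so that it declares and justifies any protocol analysis still omitted, including the analysis against pre-defined levels of change.

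Housekeeping while the text is open, none of it bearing on the conclusion: 7.1.1 refers to a central laboratory where the protocol uses local ranges; no table title says where coagulation is reported; the protocol's 95% confidence intervals for vital-sign and ECG means are not planned, though they follow from n, mean and SD.

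The cost is programming for four panels and some SAP wording. All of it uses data already collected.

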7.10 Electrocardiogram

Electrocardiogram (Standard 12-lead ECGs) at each visit will be classified as:

- Normal
- Abnormal, i.e. changes Not Clinically Significant
- Abnormal, i.e. changes Clinically Significant

Summary statistics (n, mean, SD, median, quartiles, minimum, maximum) of ECG parameters will be presented at each assessment time point.

Summary statistics of change from baseline of ECG parameters (including heart rate (HR), RR interval, PR interval, QRS width and QT/QTc interval) will also be presented.

7.11 Vital Signs

Summary statistics (n, mean, SD, median, quartiles, minimum, maximum) of vital signs will be presented at each assessment time point. Summary statistics of changes from baseline will also be presented.

Number and percentage of subjects with shift changes from baseline will be tabulated in Shift Tables for each vital sign assessment.

The following normal ranges for vital signs will be used:

Systolic blood pressure	BETWEEN 90 AND 150 (mm Hg)
Diastolic blood pressure	BETWEEN 45 AND 90 (mm Hg)
Heart Rate	BETWEEN 40 AND 100 (beats/min)

Listings of all vital signs will be presented.

7.12 Physical Examinations

Summary statistics (n, mean, SD, median, quartiles, minimum, maximum) of weight and BMI will be presented at each assessment time point.

Physical examination data from complete physical examinations will be listed by subject.

7.13 Prior and Concomitant Medications

Prior and Concomitant medications will be presented grouped by RA/AS patient disease groups and total using summary tables and will be classified according to whether they were taken before baseline or either started or taken during the study period.

Number and percentage of subjects will be summarized by World Health Organization Drug Dictionary Enhanced (WHO DDE version Q3 2017), and grouped by ATC code level 3.

Use of concomitant medications will also be presented in listings by subject.

Medications will be defined as prior if stop date is not missing, and less than the date of the first administration of the investigated imaging product, concomitant otherwise.

Medications will be considered as both prior and concomitant when the start date is before the administration of the investigated imaging product and stop date is after the administration of the investigated imaging product, or unknown or marked as ongoing and when the start date is unknown and the stop date is after the administration of the investigated imaging product, or marked as ongoing.

Medications with incomplete start or stop dates will be considered concomitant medications if it is possible that they could have been concomitant medications.

7.14 Pharmacokinetics and Dosimetry

Standard non-compartmental analysis will be conducted for the calculation of usual pharmacokinetic parameters such as AUC, Vz, Cl and elimination half-life, using serum concentration-time data. Mean serum area under the concentration-time curve will be determined using the linear trapezoidal rule and extrapolated to infinity using the plasma elimination rate constant.

All pharmacokinetic parameters will be calculated for each subject, and summary statistics (n, mean, SD) will be tabulated.

The quantitative in vivo biodistribution of the ^{99m}Tc -rhAnnexin V-128 will be determined through whole-body planar imaging. In addition, a SPECT/CT will be performed by regions in order to generate relevant dosimetry data after extrapolation for the reconstruction with OLINDA software.

Radiation dose to the organ of interests (particularly the kidneys), effective dose equivalent and effective dose will be calculated following the MIRD committee guidelines using the OLINDA/EXM software.

Summary statistics (n, mean, SD, median, quartiles, minimum, maximum) of PK and dosimetry parameters will be tabulated.

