4.4 Treatment

The single dose vial (rhAnnexin V-128: 0.40 mg) will be reconstituted with 740 MBq (20 mCi) of ^{99m}Tc . The labelling reaction requires 90 minutes and the reconstituted radiolabelled product is stable for 6 h. For the purpose of this study, it is recommended to administer the reconstituted solution within 4 hours after completion of the labelling reaction. The drug is administered at a dose of 250 MBq as a single intravenous bolus over 10-20 seconds at Day 1 and at 6 weeks (42 days) +/- 2 weeks after the first administration.

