4.10 Pharmacokinetics and Dosimetry

For first 3 patients included into the subgroup of PK and dosimetry study, blood sample will be collected at Day 2 For the first 3 patients participating to the PK substudy, a further 10 ml of venous blood samples will be drawn at nominal times of 0, 5, 10, 15, 30, 60 minutes as well as 2 hrs, 4hrs and 24 hrs post administration. Depending upon the results in those 3 patients, the timeframe for dosimetry measurements and PK will be confirmed or modified with a time-point at 3 hrs (instead of 2 hrs) and 6 hrs (instead of 4 hrs) for the following 7 enrolled patients in the sub-study.

Urine sample will be collected within 24 hrs prior to ^{99m}Tc -rhAnnexin V-128 administration, preferable just prior to its administration (0 h sample) to achieve bladder emptying. Urine collections will be obtained and volume recorded, possibly in the time intervals 0-1 h, 1 h – 4 hrs, 4 hrs -16 hrs, 16 hrs – 24 hrs post administration. Dual 2 mL aliquots of urine from each period will be counted in a gamma counter at local laboratory

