7.1.2 Handling of Missing Data and Data from Unscheduled or Repeat Visits

No imputations of missing data will be used in the analysis of safety data and PK/Dosimetry. In particular for PK, a minimum number of 3 valid time points is required for including the subject in the PK analysis.

For summary statistics, only data from scheduled visits will be used. Data from unscheduled visits or repeat tests will not be used when descriptive statistics are presented by visit. However, all observed data including repeat tests and unscheduled visits will be presented in assessments of max and min changes on treatment, shift tables and in listings. Missing data will appear as blank.

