10.2 List of Figures

Number	Figure Title	Analysis Set	Shell type
14.2.1	Annexin V-128 serum time-concentration linear graphs	PK	1
14.2.2	Annexin V-128 serum time-concentration semilog graphs	PK	1
14.2.3	Annexin V-128 serum Area Under the Curves	PK	2
14.2.4	Radioactivity levels in whole blood samples graph	PK	1
14.2.5	Radioactivity levels in serum samples graph	PK	1
14.2.6	Radioactivity levels in urine samples graph	PK	1
14.3.1	ECG parameters change from baseline box plot	Safety	3

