**STA01form01v3**

Advanced Accelerator Applications
Protocol: AAA-1001

Table 14.2.4: Summary of Serum concentrations (ng/mL) of rhAnnexin V-128 based on ELISA analysis
Population: PK (N=xx)

Timepoint	Statistic	V-128 (N=xxx)
Before treatment	n	xxx
	Mean (SD)	xx.xx (xx.x)
	Geometric mean (CV)	xx.xx (xx.x)
	Median	xx.x
	Min, Max	xx.x, xx.x
5 minutes	n	xxx
	Mean (SD)	xx.xx (xx.x)
	Geometric mean (CV)	xx.xx (xx.x)
	Median	xx.x
	Min, Max	xx.x, xx.x
10 minutes	n	xxx
	Mean (SD)	xx.xx (xx.x)
	Geometric mean (CV)	xx.xx (xx.x)
	Median	xx.x
	Min, Max	xx.x, xx.x

Data source: listings 16.X.X
Source code: xxxx.ssc. Date/time of run: DDMMYYYY:HH:MM.

Page X of Y

Table 14.2.5: Summary of Volume of distribution (Vz) and systemic clearance (Cl) of rhAnnexin V-128
based on ELISA analysis.

[figure not shown]
Population: PK (N=xx)

Parameter	Statistic	V-128 (N=xxx)
Volume of distribution (Vz)	n	xxx
	Mean (SD)	xx.xx (xx.x)
	Geometric mean (CV)	xx.xx (xx.x)
	Median	xx.x
	Min, Max	xx.x, xx.x
systemic clearance (Cl)	n	xxx
	Mean (SD)	xx.xx (xx.x)
	Geometric mean (CV)	xx.xx (xx.x)
	Median	xx.x
	Min, Max	xx.x, xx.x

Data source: listings 16.x.x

Source code: xxxx.ssc. Date/time of run: DDMMYYYY:HH:MM.

Page X of Y

STA01form01v3

Advanced Accelerator Applications
Protocol: AAA-1002

[figure not shown]
Table 14.2.6 Summary of SEC-HPLC analysis results
Population: PK (N=xx)

Species found	Visit	Statistics	Score
XXXXXX	Day 1	n	XXX
		Total	XXXXXX
		Mean	XXX.X
		SD	XXX.XX
		Median	XXX.X
		Min, Max	XXX, XXX
	24 Hours	n	XXX
		Total	XXXXXX
		Mean	XXX.X
		SD	XXX.XX
		Median	XXX.X
		Min, Max	XXX, XXX

Data source: listing 16.x.x.x

Source code: xxxx.ssc. Date/time of run: DDMMYYYY:HH:MM

Page X of Y

STA01form01v3

Advanced Accelerator Applications

Protocol: AAA-1002

Table 14.3.1.1 Overall Summary of TEAEs
Population: Safety (N=xx)

AE Category	RA (N=xx) n (%) [Events]	AS (N=xx) n (%) [Events]	V-128 Total (N=xx) n (%) [Events]
Treatment emergent AEs	xx (xx.x) [xx]	xx (xx.x) [xx]	xx (xx.x) [xx]
Treatment emergent adverse drug reactions	xx (xx.x) [xx]	xx (xx.x) [xx]	xx (xx.x) [xx]
Treatment emergent SAEs	xx (xx.x) [xx]	xx (xx.x) [xx]	xx (xx.x) [xx]
Treatment emergent serious adverse drug reactions	xx (xx.x) [xx]	xx (xx.x) [xx]	xx (xx.x) [xx]
Treatment emergent AEs leading to withdrawal	xx (xx.x) [xx]	xx (xx.x) [xx]	xx (xx.x) [xx]
Treatment emergent AEs leading to death	xx (xx.x) [xx]	xx (xx.x) [xx]	xx (xx.x) [xx]
...			

Data source: Listing 16.2.x.x.x

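### SAP 7.14 fixes a linear trapezoid across the 4 h (or 6 h) to 24 h gap after an IV bolus; if the 24 h ELISA value is quantifiable and the half-life is roughly 4 to 8 h, serum AUC is overstated and Cl and Vz understated

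*SAP*

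**What the plan says.** SAP 4.4 gives the route: "The drug is administered at a dose of 250 MBq as a single intravenous bolus over 10-20 seconds". SAP 4.10 has sub-study blood drawn at "nominal times of 0, 5, 10, 15, 30, 60 minutes as well as 2 hrs, 4hrs and 24 hrs post administration" in the first 3 patients. For the following 7, the 2 h and 4 h samples may be moved to 3 h and 6 h. Protocol section 6 (Pharmacokinetics) shows that the time-0 sample is taken just before dosing.

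SAP 7.14 applies non-compartmental analysis to serum concentrations, with parameters calculated for each subject. AUC "will be determined using the linear trapezoidal rule and extrapolated to infinity using the plasma elimination rate constant". No log-down option and no rule for C0 is given. SAP 6.2 lists "Annexin PK parameters: AUC, Vz, Cl and elimination" half-life for the ELISA data, and Table 14.2.5 is the "Summary of Volume of distribution (Vz) and systemic clearance (Cl) of rhAnnexin V-128". SAP 7.1.2 adds only that "a minimum number of 3 valid time points is required for including the subject in the PK analysis". That decides who enters the analysis, not how the area is computed.

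Protocol section 8 (Pharmacokinetics and immunology) announces a separate PK/immunology analysis plan. It is not among the documents.

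**The concern.** After a bolus, serum levels fall roughly exponentially. The linear rule joins neighbouring samples by straight lines, which lie above a convex falling curve. Over the early, closely spaced samples this hardly matters. Over a last interval of 20 h (4 to 24 h) or 18 h (6 to 24 h) it can, because the true curve drops soon after the interval opens while the line carries area across all of it.

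The excess always has the same sign, so more patients would not average it out. Cl is dose divided by AUC and is low by the matching factor. Vz is Cl divided by λz and follows when λz is close to unbiased. If the schedule is modified after the first 3 patients, the size of the error also differs between them and the next 7.

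**Working it through.** The plan states no AUC, Cl, half-life or assay limit, so there is no figure of its own to reproduce. The check applies the planned rule to known curves at the planned times.

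**Inputs from the documents.** IV bolus; pre-dose sample; 5, 10, 15, 30 and 60 min; then 2, 4, 24 h (schedule A) or 3, 6, 24 h (schedule B).

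**Assumptions.** The 24 h value is quantifiable; terminal half-life h is 2 to 12 h; λz comes from a log-linear fit of the last three points.

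**Formulas.** C(t) = a·e^(−αt) + (1−a)·e^(−βt) with C0 = 1; a = 0 is mono-exponential with β = ln 2 / h.
- True AUC = a/α + (1−a)/β.
- Planned AUC = sum of (t₂−t₁)(C₁+C₂)/2, with the pre-dose zero at time 0, plus C(24)/λz.
- Cl ratio = 1/(AUC ratio). Vz ratio = 1/(AUC ratio × λz ratio).

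**One case by hand, h = 4 h.** True AUC = 4/ln 2 = 5.771.
- Schedule A, 4 to 24 h: C(4) = 0.5 and C(24) = 0.015625. Linear area = 20 × 0.515625/2 = 5.156. True area = (0.5 − 0.015625)/0.1733 = 2.795. The interval is overstated 1.84-fold; the excess of 2.361 is 41% of the true AUC.
- Schedule B, 6 to 24 h: C(6) = 0.3536. Linear area = 18 × 0.3692/2 = 3.323, against a true 1.950, or 1.70-fold. The excess of 1.373 is 24% of the true AUC.

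Over all intervals the ratios are 1.40 and 1.24, so almost all of the error comes from the last interval.

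**Mono-exponential decline** (Cl from unrounded ratios):

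| Half-life | 24 h level, % of C0 | AUC ratio A | Cl A | AUC ratio B | Cl B |
|---|---|---|---|---|---|
| 2 h | 0.024 | 1.62 | −38% | 1.29 | −22% |
| 3 h | 0.39 | 1.53 | −35% | 1.29 | −22% |
| 4 h | 1.6 | 1.40 | −29% | 1.24 | −19% |
| 5 h | 3.6 | 1.30 | −23% | 1.19 | −16% |
| 6 h | 6.3 | 1.23 | −19% | 1.15 | −13% |
| 8 h | 12.5 | 1.14 | −12% | 1.09 | −8% |
| 12 h | 25 | 1.06 | −5% | 1.04 | −4% |

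λz is exact here, so Vz is low by the same percentages. Linear-up/log-down with C0 back-extrapolated from 5 and 10 min gives 1.00 in every row. Keeping the linear rule but back-extrapolating C0 changes little (1.41 and 1.25 at 4 h), so in this table the trapezoid rule is the cause.

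**Adding a fast phase, slow half-life 2 to 8 h:**

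| Fast phase | Rule and C0 | A | B |
|---|---|---|---|
| 0 to 80% of C0, 10 or 20 min | linear, pre-dose zero | 1.11 to 1.62 | 1.08 to 1.29 |
| same | log-down, pre-dose zero | 0.96 to 1.00 | 0.96 to 1.00 |
| same | log-down, back-extrapolated | 1.00 to 1.02 | 1.00 to 1.03 |
| 95% of C0 | linear, pre-dose zero, lowest | 1.07 | 1.05 |
| 95% of C0 | log-down, pre-dose zero, lowest | 0.91 | 0.92 |
| 95% of C0 | log-down, back-extrapolated | up to 1.02 | up to 1.05 |

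In the 0 to 80% rows under the planned rule, λz is 1.00 to 1.02 times true.

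**No quantifiable 24 h value.** Mono-exponential, half-lives 1 to 12 h: linear AUC ratio 0.995 to 1.013 (A) and 0.998 to 1.069 (B). Bi-exponential example (80% fast at 20 min, slow 6 h, A): AUC 0.72 linear and 0.73 log-down, λz 2.14 times true. Under the linear rule Cl is 39% high (1/0.72) and Vz 35% low (1/(0.72 × 2.14) = 0.65). The trapezoid rule is almost irrelevant there.

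**The case against.** **The error is conditional.** A reader might infer that the Cl and Vz in Table 14.2.5 will be wrong as planned. The documents do not support that: half-life and assay limit are not given, the effect is small at 12 h, and for mono-exponential decline it is small when the 24 h value cannot be quantified. This stands and limits the claim.

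**The largest figures are the least likely.** A reader might also take the 38% Cl error at 2 h as the headline. It needs an assay that can read 0.024% of C0, so it is an upper bound. A dominant fast phase makes the demand stricter: with 80% of C0 in it, the 24 h level at a 4 h slow half-life is about 0.3% of C0. This stands too.

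**C0 is a separate defect.** With a very steep fast phase, using the pre-dose zero costs up to 9% under log-down, comparable with the trapezoid error itself. It stands, and is why the fix has two parts.

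**Another document may govern PK.** SAP section 2 describes its purpose as safety and tolerability, and the announced PK plan could hold rules for C0, values below the limit and λz. That cannot be checked. SAP 7.14 nevertheless names a rule explicitly and does not defer to that plan, so the two should agree.

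**Low stakes.** Linear trapezoid is a recognised option. The parameters are secondary and descriptive, in at most 10 patients, and nothing in the documents ties a decision to Cl or Vz. Serum results are listed (Listing 16.2.6.1), concentrations are tabulated (Table 14.2.4), and "Annexin V-128 serum time-concentration semilog graphs" are planned, so AUC can be recomputed. This limits the importance, not the correctness, of the point.

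**Conclusion.** The point holds conditionally. If the 24 h ELISA value is quantifiable and the terminal half-life is roughly 4 to 8 h (both assumptions), mono-exponential AUC is overstated by about 14% to 40% on 2/4/24 h and 9% to 24% on 3/6/24 h. Cl is about 12% to 29% and 8% to 19% low, with Vz similar when λz is close to unbiased. At 2 h the AUC error would reach 62% and 29%, as an upper bound. With 95% of C0 in a fast phase and the pre-dose zero kept, the smallest overstatement at 2 to 8 h is about 7% and 5%. At 12 h it is 6% and 4% for mono-exponential decline.

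Table 14.2.5 would report biased Cl and Vz under these conditions, not in every case. With bi-exponential decline and no usable 24 h value, λz is the main problem and no trapezoid rule cures it. The point concerns the ELISA serum AUC only. The choice of rule does not change λz or half-life, and radioactivity AUC and dosimetry are outside it. It is worth correcting before the PK tables are run, but does not touch the primary safety objective.

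**What to change.** In SAP 7.14:
- Replace the linear rule with linear-up/log-down for each patient's serum AUC.
- Set C0 by log-linear back-extrapolation of the 5 and 10 min samples, not the pre-dose value. Both changes are needed: in the scenarios above, log-down with the pre-dose zero is up to 4% low (up to 9% low with a 95% fast phase), against 0% to about 5% high with back-extrapolated C0.
- Beside Cl, Vz and half-life, show the extrapolated fraction of AUC and the points used for λz.
- Flag, but do not remove, patients without a quantifiable 24 h value.
- Keep the text consistent with the PK/immunology plan announced in protocol section 8.

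The cost is SAP wording and a software setting, with no new samples and no patient dropped from the tables.
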